5.1. General Considerations

- The primary analysis will be performed after the database is locked and randomization schedule is released.
- To account for different timing of VOLITE treatment and comparable time frame of data collection to enhance interpretability of effectiveness and safety analyses, the statistical analyses will be performed by the study periods defined below in [Table 5-1](#). For participants randomized to the treatment group, the Treated Period (TP) is the Control Period (CP) plus the Follow-up Period; for participants randomized to the control group, the TP is the Follow-up Period composed of the delayed treatment period plus the delayed treatment follow-up period ([Figure 1-1](#)). Follow-up Period starts on the end date of CP + 1 and ends on the same day as TP.

Table 5-1 Definition of the Control, Treatment, and Repeat Treatment Periods by Randomization Group

Randomization Group	Period	Treatment Group Label	Start Date	End Date
Treatment	Control Period (CP)	VOLITE	Initial treatment date	
The end date is the date of the Month 1 assessment:
 
 • If multiple assessments fall into Month 1 window, the date of the assessment included in the Month 1 analysis will be used as end date. • For participants who exit before Month 1, the end date is study exit date. • For participants with a missing assessment at Month 1, the end date is the target day for Month 1.
	Treated Period (TP)	VOLITE	Initial treatment date	Date of repeat treatment or the study exit date, whichever is earlier
	Repeat Treatment Period (RP)	VOLITE	Repeat treatment date	Study exit date
Control	CP	Control	Randomization date	
For participants who do not receive optional treatment:
 
 • If multiple assessments fall into Month 1 window, the date of the assessment included in the Month 1 analysis will be used as end date. • For participants who exit before Month 1, the end date is study exit date. • For participants with missing assessment at Month 1, the target day for Month 1 (Day 31) will be the end date. 
For participants who receive optional treatment: the end date is the date of optional treatment.

	TP	VOLITE Post-Control	Optional treatment date	Study exit date

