5.6.3. Adverse Events

An AE will be considered a treatment emergent adverse event (TEAE) if the AE began or worsened (increased in severity or became serious) after first administration of VOLITE for the treatment group and after the date of randomization for the control group. A TESAE is defined as an SAE that is also a TEAE. Overall summary will be provided on a per-participant level for TEAEs, treatment-related TEAEs, TESAEs, deaths, and TEAEs leading to study intervention discontinuation.

If more than one event is coded to the same PT for the same participant, the participant will be counted only once for that PT using the greatest severity for the summarizations by severity and most related occurrence for the summarizations by relationship to study intervention. If the severity of a TEAE is missing, the maximum severity will be assigned to the event for the summarization by severity. The value will be displayed as missing in the data listing. If the relationship to the study intervention is missing for a TEAE, the event will be considered related to the study intervention for the summarization. The value will be displayed as missing in the data listing.

TEAEs will be summarized by treatment group for CP using the Safety population. TEAEs will also be summarized for TP and RP using the VT and VRT populations, respectively.

The number and percentage of participants with TEAEs and the events in the following AE categories will be summarized for the above populations as described in [Table 5-8](#). For participants who received repeat treatment, their AEs reported during the first month in the initial treatment period will be summarized and presented in parallel with AEs reported during the repeat treatment period.

JUVÉDERM VOLITE™ XC

Summary tables will be provided for participants with TESAEs and participants with TEAEs leading to discontinuation if these occurred in 5 or more participants. Listings of all TEAEs, AESIs, TESAEs, TEAEs leading to discontinuation, and death will be presented.

Table 5-8 **TEAE Summaries**

Endpoint	Description	Timing	Methodology

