5.6.4. Injection Site Response

ISRs recorded in participant diaries after each treatment (initial, touch-up or repeat) and the ongoing ISR e-CRF will be summarized. The diary date and time will be compared with the treatment injection date and time recorded in the database to determine the corresponding treatment (ie, initial, touch-up, or repeat) for the purpose of analysis. If there are multiple diary entries of the same treatment period for any day, then the worse severity and maximum duration

JUVÉDERM VOLITE™ XC

will be included in the summary for the corresponding symptom(s) analyzed. The descriptive statistics will be tabulated for the endpoints listed in Table 5-9 for the initial treatment, touch-up treatment, and repeat treatment periods by pre-defined symptoms.

Table 5-9 **Injection Site Response Analyses**

Endpoint	Description	Timing	Methodology
ISR severity	
Maximum reported severity for 2 summaries listed below:
 
 Up to 30 days after the treatment (initial, touch-up or repeat) based on diary data only Beyond 30 days after the (initial, touch-up or repeat) treatment across the diary and ongoing ISR eCRF 	Initial, Touch-up, Repeat	Frequency counts and percentages
ISR duration	
Duration from first instance of the symptom to the last instance of the symptom within the treatment period for 2 summaries listed below:
 
 Up to 30 days after the treatment (initial, touch-up or repeat): duration is derived as date of last ISR minus date of first ISR plus one based on the diary data between the date of corresponding treatment and 30 days after it on the participant level, regardless of the side of cheek. Beyond 30 days after the (initial, touch-up or repeat) treatment: duration is calculated as the last minus the first ISR occurrence date plus one based on all data collected from diary and ongoing ISR eCRF. 	Initial, Touch-up, Repeat	Frequency counts and percentages

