6.4.2. Missing Date Imputation

Missing date will be imputed for TEAEs and medications. The missing AE dates will be imputed with year, month, and day values based on the corresponding scenarios in [Table 6-5](#) and algorithms described in [Sections 6.4.2.1](#) and [6.4.2.2](#). If the AE stop date is complete and the imputed AE start date is after the stop date, the AE start date will be re-imputed using the stop date. If the imputed AE stop date is before the start date (imputed or non-imputed start date), the start date will be the imputed stop date.

The missing medication start and stop dates will be imputed based on the algorithms described in [Sections 6.4.2.3](#) and [6.4.2.4](#). When the medication start date and stop date are both incomplete for a participant, the start date will be imputed first. If the medication stop date is complete and the imputed start date is after the stop date, the start date will be imputed using the stop date. If the imputed medication stop date is before the start date (imputed or non-imputed start date), the start date will be the imputed stop date.

Table 6-5 **Imputation Scenarios**

Scenario	Complete			Imputable
	Year	Month	Day	
1	Yes	Yes	Yes	N/A
2	Yes	Yes	—	Yes
3	Yes	—	Yes	No ^a
4	Yes	—	—	Yes
5	—	Yes	Yes	No ^a
6	—	Yes	—	No ^a
7	—	—	Yes	No ^a
8	—	—	—	Yes

^a Not allowed per database design.

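### SAP Table 5-1 ends the control group's Control Period on the day of the optional injection, so adverse events that start after that injection are tabulated under no treatment

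*SAP*

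**What the plan says.** SAP section 5.1 divides each participant's time into a Control Period (CP), a Treated Period (TP) and a Repeat Treatment Period (RP).

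- **Table 5-1, control group, CP (label Control), end date:** "For participants who receive optional treatment: the end date is the date of optional treatment".
- **Table 5-1, control group, TP (label VOLITE Post-Control), start date:** "Optional treatment date".
- **Text above the table:** "for participants randomized to the control group, the TP is the Follow-up Period", and "Follow-up Period starts on the end date of CP + 1 and ends on the same day as TP".

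SAP section 5.6.3 counts an AE as treatment-emergent if it began or worsened "after first administration of VOLITE for the treatment group and after the date of randomization for the control group". It then says: "TEAEs will be summarized by treatment group for CP using the Safety population". TP events are tabulated for the VOLITE Treated population.

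The AE date rules in section 6.4.2 work in whole days: "The missing AE dates will be imputed with year, month, and day values". Only injection site responses (ISRs) are placed by clock time. Section 5.6.4 compares each diary entry with the "treatment injection date and time recorded in the database to determine the corresponding treatment".

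**The concern.** The table and the text give different first days for the control group's TP, and the day in dispute is the injection day. Both cannot be programmed. The text also conflicts with itself, because its Follow-up Period includes the delayed treatment period yet begins the day after that treatment.

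The larger problem is common to both versions: CP includes the injection day. A control who was untreated for a month and is then injected is still labelled Control for the rest of that day. Events that follow the injection count towards the untreated arm.

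That day is likely to matter. Protocol section 9.5 lists redness, swelling, pain and bruising after injection as known potential AEs. Protocol section 9.4 lets the treating investigator decide whether an ISR qualifies as an AE. Vision checks, which bear on the one AE of special interest, are repeated about 30 minutes after injection (Protocol Table 2-4).

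CP is the only period in which VOLITE and no treatment are compared as randomized. Misplaced events raise the Control rate and shrink the apparent difference. Under the text's version they are also missing from the TP rates.

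**Working it through.** **Date logic.** Let the optional injection fall on day T, counted from randomization as day 1. The sentence that starts follow-up on the day after CP ends shows that the CP end date is inclusive.

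| Source | CP (Control) | TP (VOLITE Post-Control) | AE starting on day T |
|---|---|---|---|
| Table 5-1 | 1 to T | T to exit | In CP and in TP |
| Text of 5.1 | 1 to T | T + 1 to exit | In CP only |

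Checking T = 31 and T = 38 gives the same pattern.

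**Does another rule remove the event from CP?**

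- Section 5.6.3 counts control events from randomization, with no cut at the optional injection.
- Section 6.4.2 uses year, month and day, so it cannot order events within a day.
- The as-treated assignment in Table 4-1 classifies participants. It does not reassign the events of a control treated as planned.
- The mis-treatment rule in 5.1 covers controls injected before the primary timepoint, not those injected on schedule.
- The date-and-time rule in 5.6.4 covers ISRs only. The ISR tables are therefore not affected.

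None does.

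**Inputs for size.** SAP section 3 gives 210 randomized at 2:1 and 119 + 28 = 147 treated participants, 28 of them controls. As a check on the source of the 28, the stated 95% power to see an AE of 2% incidence among 147 reproduces: 1 − 0.98^147 = 0.949.

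- Controls: 210 / 3 = 70.
- Share expected to be injected: 28 / 70 = 40%.

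**Size.** Let p be the probability that an injected control has an AE starting on the injection day. The documents do not give p, so 2% to 30% is assumed. Participants added to the Control column are 28 × p. The rise in the Control rate is 28 × p / 70. Under the text's version, the shortfall in TP is 28 × p / 147.

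| p | Added to Control | Rise in Control rate (points) | Shortfall in TP, text version (points) |
|---|---|---|---|
| 2% | 0.56 | 0.8 | 0.4 |
| 10% | 2.8 | 4.0 | 1.9 |
| 30% | 8.4 | 12.0 | 5.7 |

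The chance of at least one misplaced participant is 1 − (1 − p)^28. This is 1 − 0.98^28 = 0.43 at 2%, and 1 − 0.90^28 = 0.95 at 10%.

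These are upper bounds for each p. They assume that no such participant already had an AE in CP and that every injection-day AE began after the injection.

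**The case against.** The strongest reply is that the intent is clear and the text is a slip. Section 5.1 says the analyses follow the periods in Table 5-1, and that table puts the injection day in TP. Table 4-1 describes optional treatment as coming after the Control Period. Protocol Table 2-4, note a, offers it only once the one-month control period is complete. On this reading no event is lost from TP, and the fault is a double count.

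This makes the table the likelier rule for TP, so the loss from TP is the less likely outcome. It does not repair CP, whose stated end date is the injection day in the same table. The passages that show the intent conflict with that date.

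A second reply is that section 5.6.3 never says AEs are assigned to periods by onset date, that AE onset time may be collected, and that table specifications sit in a separate document. That is possible, but the SAP states no such rule, and where it wanted clock time, for ISRs, it said so.

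A third reply concerns size. Many injection-day reactions will stay in the diary as ISRs, so the upper end of the assumed range may be too high. AE output is descriptive, with no test attached. All treatment-emergent AEs are listed, and the CP summary has treatment-related rows split by injection site, so an odd event under Control could be noticed. These points limit the consequence. The column total would still be wrong.

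**Conclusion.** The concern holds. Followed as written, SAP Table 5-1 places post-injection events of treated controls in the no-treatment column of the only randomized AE comparison. The table also counts them in TP; the text leaves them out of TP.

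The date conflict rests on the SAP's wording alone. The size rests on the planned 28 treated controls of 70 and on an assumed injection-day AE probability. Even at the low end of that assumption, at least one misplaced participant is close to an even chance.

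The matter should be corrected, but it is not critical. Sample size, alpha, power and the primary and secondary effectiveness analyses do not change. The same one-day overlap exists where TP ends and RP begins, on the repeat-treatment date. It is minor, because both periods are VOLITE-treated.

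**What to change.** In SAP section 5.1 and Table 5-1:

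1. For AE analyses, end the control group's CP before the optional injection. Assign AEs with onset after the injection on that day to TP only. Where the order cannot be established, assign the AE to TP.
2. Apply the same AE rule at the TP/RP boundary.
3. Correct the Follow-up Period sentence so that control TP starts on the optional-treatment date, as the table has it.
4. Keep the present date limits for effectiveness, so that ratings made before the injection on the same day stay in the earlier period. The control Month 1 rating then remains in CP (Table 6-3). The Month 6 rating remains in TP when Month 6 is the repeat-treatment visit (Table 6-2; Protocol Table 2-2, note c).
5. As a clarification only, state that optional delayed treatment is not a first treatment within the control period for the baseline definition in 5.1. Baseline for correctly treated controls is then the randomization value. Keep the existing rule that takes the later of the two dates for mis-treated participants.

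The cost is a few lines of SAP text and derivation code. The one drawback is that a same-day AE that began before the injection, but whose order was not recorded, would be attributed to TP.

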Procedure	Randomization ^a	Month 1 Study Exit visit
Visit Window (Days)		-2/+7
Urine pregnancy test ^b	X	
Inclusion/Exclusion criteria (TI, EI, Subject)	X	
FACE-Q Satisfaction with Skin questionnaire (Subject)	X	X
FACE-Q Appraisal of Lines-Overall questionnaire (Subject)	X	X
ACSS (EI)	X	X
AFLS (EI)	X	X
Skin hydration (EI)	X	X
2D facial imaging	X	X
Randomization	X	
Weight measurement		X
Concomitant medications, procedures, treatments	Continuous Monitoring	
Adverse events	Continuous Monitoring	

^a Randomization must occur within 30 days of screening; screening visit and randomization visit can occur on the same day if subjects do not require washout. If screening and randomization visits occur on the same day, inclusion/exclusion criteria and urine pregnancy testing need not be repeated.

^b For female subjects of childbearing potential; administered and confirmed negative prior to randomization. A female subject is not considered of childbearing potential if she has been postmenopausal for at least 1 year or does not have a uterus at the time of study entry.

Table 2-4 Control Group Procedures (Delayed Treatment Period)

Procedure	Initial Tx ^a	Day 3 after Initial Tx	Touch-up Tx Day 30 ^b	Day 3 after Touch-up Tx	Month 1	Month 2	Month 4	Month 6 Study Exit Visit
Visit Window (Days)	+7	+2	-2/+7	± 2	-2/+7	±7	±7	±7
Urine pregnancy test ^c	X		X					X
Snellen visual acuity (TI or designee)	X ^d	X	X ^d	X	X			
Confrontational visual fields (TI or designee)	X ^d	X	X ^d	X	X			
Ocular motility (TI or designee)	X ^d	X	X ^d	X	X			
Treatment procedure ^e	X		X					
Procedural pain	X							
Safety e-diary ^f (Subject)	X		X					
FACE-Q Recovery Early Life Impact questionnaire (Subject)		X						
2D facial imaging		X	X		X	X	X	X
FACE-Q Satisfaction with Skin questionnaire (Subject)			X		X	X	X	X
FACE-Q Appraisal of Lines-Overall questionnaire (Subject)			X		X	X	X	X
Natural look and feel assessment (Subject)			X		X	X	X	X
GAIS (Subject)			X		X	X	X	X
ACSS (EI)			X		X	X	X	X
AFLS (EI)			X		X	X	X	X
Skin hydration (EI)			X		X	X	X	X
Weight measurement								X
Concomitant medications, procedures, treatments					Continuous Monitoring			
Adverse events					Continuous Monitoring			

^a Initial treatment for the control group is offered only after completion of 1 month of no-treatment control period.

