7.4 Method of Treatment Assignment and Allocation Ratio

Prior to initiation of study treatment, each consented subject will be assigned a subject number that will be recorded on the appropriate eCRF. At the time of randomization (ie, at the Randomization/Initial Treatment visit), eligible subjects will be randomly assigned at a 2:1 ratio to treatment group or control group. Randomization will be within each study site. All subjects will be centrally randomized using an IWRS. Before the study is initiated, the log-in information and directions for the IWRS will be provided to each site. If subjects are withdrawn, they will not be replaced.

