The primary effectiveness variable is the cheek skin smoothness based on the ACSS evaluated by EIs. The primary effectiveness endpoint is the ACSS responders at Month 1 defined as a participant who achieves at least a 1-point improvement from baseline on both cheeks based on ACSS. Month 1 refers to 1 month after the preceding treatment (initial or touch-up) for participants in the JUVÉDERM VOLITE XC treatment group or 1 month after randomization for participants in the no-treatment control group.

The null hypothesis is that there is no difference between the JUVÉDERM VOLITE XC treatment group and the no-treatment control group in the ACSS responder rate at Month 1. The alternative hypothesis is that there is difference between the JUVÉDERM VOLITE XC treatment group and the no-treatment control group in the ACSS responder rate at Month 1. These hypotheses are stated as:

$$H_0: P_v - P_c = 0$$

$$H_a: P_v - P_c > 0 \text{ or } P_v - P_c < 0$$

where P_v and P_c denote the responder rates for the JUVÉDERM VOLITE XC group at Month 1 after the preceding treatment (initial or touch-up) and for the no-treatment control group at Month 1 after randomization, respectively. The treatment effects between JUVÉDERM VOLITE XC and the no-treatment control group will be compared using the statistical method described in [Section 5.3.2](#). If the 2-sided p-value is less than 0.05 and the responder rate is greater for JUVÉDERM VOLITE XC than for the no-treatment control group, then JUVÉDERM VOLITE XC will be considered superior to the no-treatment control group.

3. Sample Size Determination

A sample size of 112 participants in the treatment group and 56 participants in the control group will provide 99.9% power to detect a difference of at least 40% in the responder rates on the ACSS between the groups, based on a 2-sided Fisher's exact test at the 5% level. The treatment group is assumed to have at least an 80% responder rate at Month 1, and the control group is assumed to have at most a 40% responder rate. The assumptions of responder rates are estimated from Allergan Study V12-001. Accounting for participant attrition of 20% during the study, 210 participants will be randomized at a 2:1 ratio to treatment group and control group. Randomization will occur within each study site.

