- The start and end of treatment periods listed above for the mis-treated participants (ie., randomized to Treatment and did not receive Volite or randomized to Control and was treated with Volite prior to the primary timepoint) will be determined based on the treatment received.
- For CP, effectiveness analyses and baseline characteristics will be performed on the mITT population using the “as-randomized” assignment.

JUVÉDERM VOLITE™ XC

- For TP, effectiveness and safety summaries will be performed on the VT population by treatment group.
- For RP, effectiveness and safety summaries will be performed on the VRT population.
- The baseline for applicable effectiveness endpoints and safety parameters will be the last non-missing assessment on or before the latter of randomization date or first treatment date in the control period
- The change from baseline values will be computed as the post-baseline value minus the baseline value.
- Continuous variables will be summarized by number of participants with observed values (n), mean, standard deviation (SD), median, 1st and 3rd quartiles (Q1, Q3), minimum (min), and maximum (max). Categorical variables will be summarized by the number of participants with observed values or events (n), frequency count (N1), and percentage of participants with observed values or events.
- All statistical hypothesis tests will be performed at the 2-sided 5% significance level, unless stated otherwise.
- In general, statistical analyses will be performed using SAS version 9.4 or higher. Adverse events (AEs) and medical history will be coded using the Medical Dictionary for Regulatory Activities (MedDRA) version 22.1 or higher.
- WHO Drug Dictionary will be used to code medications.

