6.2. Appendix 2: Changes to SAP Version 1 Analyses

The following are changes to [version 1](#) of SAP:

1. The naming of the analysis population for the sensitivity analysis of primary endpoint, ACSS responder status at Month 1 was changed from “Completer Population” to “Observed Primary Endpoint” in Section 4. The definition of this population refers to the completion of the primary timepoint visit (ie., Month 1 of CP). This naming change is aimed to avoid potential confusion with study completion.
2. The wordings of “overall converted score” were specified for the analyses of FACE-Q Satisfaction with Skin, FACE-Q Appraisal of Lines, and FACE-Q Recovery Early Life Impact in Sections 4, 5.4, 5.5 and 5.6.5 to enhance clarity and consistency with Appendix 6.5.
3. The cut-off for the of FACE-Q Satisfaction with Skin as one of the definitions for Fitzpatrick Safety Cohort was changed from 39 for the overall raw score to 69 for the overall converted score in Table 4-1.
4. The definition of “baseline” for the effectiveness and safety variables in Section 5.1 was changed to “the last non-missing assessment prior to the latter of randomization or first treatment in the control period” due to possibility of participants who were mis-treated (ie., either randomized to Volite but was not treated or randomized to Control but received Volite)
5. The multiple imputation for the primary effectiveness analysis described in Section 5.3.2 was revised to (1) include the baseline ACSS score and age in the model based on the correlation with the primary endpoint to be imputed (ie., ACSS score at Month 1 of CP) and (2) number of imputed dataset is increased from 5 to 30 to reduce variability and increase the efficiency of estimates
6. The derivation for skin hydration and analyses of following variables were added to other effectiveness analyses in Section 5.5:
 - a. raw value and change from baseline in ACSS
 - b. raw value and change from baseline in AFLS
 - c. item scores and aggregated categories for FACE-Q Satisfaction with Skin
 - d. item scores and aggregated categories for FACE-Q Appraisal of Lines
7. The analysis of ISR in Section 5.6.3 was revised to include: (1) ISR by maximum severity for summaries up to 30 days and beyond 30 days after treatment, (2) analysis of “other symptoms” based on the coded terms assigned by the Medical Safety Physician

JUVÉDERM VOLITE™ XC

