6.4. Data Handling Convention

6.4.1. Analysis Window

6.4.1.1. Effectiveness

Table 6-2, [Table 6-3](#), and [Table 6-4](#) below present the timepoints assigned for analyses and the corresponding range of study days for all the scheduled and unscheduled visits with complete dates. If a scheduled visit with incomplete date is available with no other visits with complete date during the visit window, then the visit with incomplete date may be used for analysis and the nominal visit will be used as the visit window (eg, if the only assessment collected for Month 2 visit window is on a Month 2 eCRF with incomplete date, then those data will be used for the Month 2 assessments).

If multiple assessments were taken within an analysis window, the assessment obtained on the day closest to the target day will be used; in the case of a tie, the assessment obtained on the later day will be used in the analysis.

Analysis visit windows for effectiveness endpoints are defined as follows:

If analysis date \geq reference date, then

$$\text{Analysis day} = \text{analysis date} - \text{reference date} + 1$$

If analysis date $<$ reference date, then

$$\text{Analysis day} = \text{analysis date} - \text{reference date}$$

Table 6-2 **Effectiveness Analysis Visit Definitions for Treatment Group and Control Group during Treated Period**

Scheduled Visit for Effectiveness Measure	Target Day of the Visit	Analysis Visit Window
Screening ^a	N/A	Screening visit; no more than 30 days prior to randomization
Baseline	N/A	Randomization/Initial Treatment visit
Last Treatment ^b	Day 1 of Last Treatment	Day 1
Month 1	Day 31 Post Last Treatment	Day 2 to Day 46
Month 2	Day 61 Post Last Treatment	Day 47 to Day 91
Month 4	Day 121 Post Last Treatment	Day 92 to Day 151
Month 6	Day 181 Post Last Treatment	Day 152 to Repeat Treatment Date (if applicable) or Study Exit Date, whichever is earlier

^a Participants may have screening and randomization on the same day. In such cases, only randomization visit is relevant

^b The last treatment refers to the latter of initial treatment or touch-up treatment (if applicable)

Table 6-3 Effectiveness Analysis Visit Definitions for Control Group during Control Period

Scheduled Visit	Target Day of the Visit	Analysis Visit Window
Randomization Day	Day 1	N/A
Month 1	Day 31	Day 2 to Optional Treatment Date or Study Exit Date, whichever is earlier.

Table 6-4 Effectiveness Analysis Visit Definitions for Treatment Group during Repeat Treatment Period

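### Controls who cross over to VOLITE keep their randomization baseline in the treated period, so change during the untreated month may be counted as response in that group's descriptive summaries

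*SAP*

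**What the plan says.** SAP 5.1 defines baseline once, for effectiveness and safety alike: "The baseline for applicable effectiveness endpoints and safety parameters will be the last non-missing assessment on or before the latter of randomization date". The full cut-off is "on or before the latter of randomization date or first treatment date in the control period". Appendix 2 of the SAP (item 4) explains that this wording was adopted "due to possibility of participants who were mis-treated". It does not mention planned crossover.

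SAP Table 6-2 covers the treatment group and also controls in the treated period. It lists the baseline visit for both as the "Randomization/Initial Treatment visit". Protocol 7.4 ties that visit to the moment of allocation: "At the time of randomization (ie, at the Randomization/Initial Treatment visit".

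Delayed treatment comes later. A footnote to Protocol Table 2-4 states: "Initial treatment for the control group is offered only after completion of 1 month of no-treatment control period". SAP Table 5-1 accordingly starts these subjects' treated period on the optional treatment date and labels them VOLITE Post-Control.

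SAP 5.1 then says: "For TP, effectiveness and safety summaries will be performed on the VT population by treatment group". SAP 5.5 and Table 5-4 report, for that period, ACSS, AFLS and composite responders, and change in ACSS, AFLS, the FACE-Q scores and hydration. They give no separate baseline for crossed-over controls. The one exception in the SAP is Snellen acuity (5.6.6), which is measured from the value before the most recent treatment.

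**The concern.** In the VOLITE arm, randomization and first injection fall on the same day (footnote to Protocol Table 2-2), so the baseline is a pre-treatment value. For VOLITE Post-Control the baseline is a month older than the treatment whose result is being described. A control who has improved by a point on both cheeks by the end of the untreated month already meets the responder definition before any product is injected. If the improvement lasts, that subject is tabulated as a responder under a VOLITE label.

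Some untreated improvement is plausible. Outside the Fitzpatrick V/VI safety cohort, entry requires an ACSS of 2 or 3 on both cheeks and a FACE-Q sum of 39 or less, so regression to the mean is expected. Subjects are also unblinded, which matters for FACE-Q. The plan's own sample size allows for untreated response: "the control group is assumed to have at most a 40% responder rate" (SAP Section 3).

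At stake is how that group's Month 1, 2, 4 and 6 summaries are interpreted.

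**Working it through.** **1. Which rating is the baseline?** A control managed as planned has no injection during the untreated month, so the later of the two dates in SAP 5.1 is the randomization date. Appendix 2 item 4, Table 6-2 and Protocol 7.4 all point the same way.

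One loose end remains. Table 5-1 ends the control period of a crossed-over control on the optional treatment date, so a literal reader could count that injection as a treatment in the control period. The Month 1 control rating would then become the baseline and these subjects would show zero change in the primary analysis. That cannot be intended.

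**2. Are pre-treatment ratings available?** Protocol Table 2-4 schedules no ACSS, AFLS, FACE-Q Satisfaction or hydration at the delayed initial treatment visit. Protocol Table 2-3 schedules all of them at the control-period Month 1 visit, just before it.

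**3. Reproduce the plan's figures.** The inputs are from SAP Section 3.
- ACSS: 80% v 40%, n = 112 v 56, two-sided Fisher's exact test at 5%. Exact enumeration gives 99.91% (stated 99.9%).
- AFLS: 80% v 45%, n = 72 v 36. Exact enumeration gives 94.40% (stated 94.4%).
- Attrition: 168 / 0.80 = 210 (stated 210).
- Safety: 1 − 0.98^147 = 94.9% (stated 95%).

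None of these is in dispute. They confirm that 40% and 45% are the untreated rates on which the plan was built.

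**4. Controls already responders at injection.** Let u be the untreated Month 1 responder rate among those who go on to treatment. The plan expects 28 of them. The count is 28 × u:

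| u | Already ACSS responders, of 28 |
|---|---|
| 5% | 1.4 |
| 10% | 2.8 |
| 20% | 5.6 |
| 40% (plan's ceiling) | 11.2 |

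For AFLS, if the plan's 65% eligibility applies to the 28: 28 × 0.65 = 18.2 eligible, and 18.2 × 0.45 = 8.2 at the ceiling.

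With the baseline taken before injection, the count at the moment of injection is zero by definition.

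**5. Illustration of the effect on a later rate.** Assume the untreated gain persists fully and is independent of response to the product. If q is the response rate from the pre-treatment baseline, the rate from the randomization baseline is 1 − (1 − u)(1 − q).
- A reported 80% at Month 1 gives q = 1 − 0.20/(1 − u): 77.8% at u = 10%, 75.0% at 20%, 66.7% at 40%.
- At Month 6, take q = 34.9%, the ACSS rate in the feasibility study (Protocol 3.2). The reported rate would be 41.4% at u = 10%, 47.9% at 20%, 60.9% at 40%.

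Under these assumptions the distortion is small at Month 1 for modest u. It is larger at late visits, where the product effect has faded.

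**The case against.** The strongest reply is that no inference rests on these summaries. The primary and both secondary endpoints are Month 1 control-period comparisons, for which the randomization baseline is the correct one. SAP 5.5 makes the treated-period effectiveness results descriptive, and crossed-over controls have their own label. This stands. A reader might infer that the rule inflates the trial's estimate of device effect or its test of superiority; the documents do not support that. Nor do they pool the two treated groups. If someone did, the carried-over responders would be at most 11.2/147 = 7.6 percentage points.

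A second reply is consistency: both groups are measured from study entry, both carry regression to the mean, and no separate effectiveness baseline is set for repeat treatment either. This stands only in part. In the VOLITE arm the entry rating immediately precedes the first injection, and the repeat-treatment period still refers back to a pre-product value. Only VOLITE Post-Control has an untreated month between baseline and product. For visual acuity the SAP already adopts the pre-treatment principle.

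A third reply concerns size, and it stands. A reader might take 11 of 28 as the expected number, or conclude that an inert product would be reported with a 40% rate. The plan says at most 40%, and the actual rate may be far lower. Rating noise need not carry the same subjects forward, those who improved untreated may be less inclined to opt for injection, and untreated skin could worsen, which would reverse the direction. The feasibility study's 15.8% ACSS responder rate at Month 9 also argues against assuming that improvement near the ceiling would persist.

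Finally, the column heading in Protocol Table 2-4 (Initial Tx) could suggest that the Table 6-2 baseline means the delayed visit. Protocol 7.4 and Appendix 2 weigh against that reading, but the text would be better if it left no choice.

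**Conclusion.** The concern holds in a limited form. As evidently intended, SAP 5.1 leaves VOLITE Post-Control subjects on their randomization baseline throughout the treated period, so change from the untreated month may be credited to VOLITE. The affected results are that group's descriptive ACSS, AFLS and composite responder rates and its change in ACSS, AFLS, FACE-Q and hydration. Scores not expressed as change from a pre-treatment value (GAIS, natural look and feel, procedural pain) and visual acuity are outside it.

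The size runs from 1.4 of 28 at 5% untreated response to 11.2 of 28 at the plan's ceiling. These counts assume that 28 controls are treated and that those who opt in have the same untreated rate as all controls. Any inflation of later rates further assumes that the untreated change persists. The point is worth settling before the tables are produced, but it does not threaten the trial's main conclusion.

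**What to change.** Make the baseline period-specific in SAP 5.1.
- State explicitly that all control-period analyses use the randomization baseline. This also closes off the literal reading of Table 5-1.
- For VOLITE Post-Control in the treated period, use the latest available rating taken no later than the first VOLITE injection, normally the control-period Month 1 value.
- Show the randomization-baseline version alongside, with both labelled in the tables.
- Bring Tables 5-1 and 6-2 into line.
- State which baseline governs the AFLS restriction (2 on both cheeks or 3 on both cheeks) and the half-standard-deviation FACE-Q threshold in the composite when these are applied in the treated period.

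No new visits or data are needed. The cost is a little more programming and a second set of columns. The pre-treatment baseline has its own limit: controls who improved untreated have less room to gain a further point, and one who reached ACSS 0 on either cheek could not respond at all. Those rates will therefore tend to be lower and may be conservative, which is the reason to show both.
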